PROTOCOL TITLE: A Multicenter Trial of Contrast-Enhanced Ultrasound in the Evaluation of Abdominal Solid Organ Injuries in Pediatric Trauma Patients

NCT NUMBER: NCT03147690

DOCUMENT DATE: 10/16/2019

PROTOCOL

PROTOCOL TITLE	A Multicenter Trial of Contrast-Enhanced Ultrasound in the Evaluation of Abdominal Solid Organ Injuries in Pediatric Trauma Patients
PROTOCOL NUMBER	P00025242
STUDY DESIGN (PHASE)	Prospective non-randomized cohort
PROTOCOL VERSION	Version 4
IND NUMBER	N/A
INVESTIGATIONAL PRODUCT	Lumason
INDICATION	To enhance visualization of abdominal solid organ injuries in children
SPONSOR	[name], MPH [name] [contact]
PRINCIPAL INVESTIGATOR	[name], MPH

Good Clinical Practices

This study was conducted under Good Clinical Practices, in accordance with the Declaration of Helsinki, in compliance with the International Conference on Harmonisation (ICH) guidelines.

Confidentiality Statement

This document contains confidential information of the Sponsor. This information is to be disclosed only to the recipient study staff and the Institutional Review Board or Institutional Ethics Committee reviewing this protocol. This information can be used for no other purpose than evaluation or conduct of this study without prior written consent from the Sponsor.

SYNOPSIS

Name of Sponsor	[name], MPH
Coordinating Center	Boston Children's Hospital
Investigational Product	Lumason
Indication (phase)	To improve ultrasound visualization of pediatric abdominal solid organ injuries
Title of Study	A Multicenter Trial of Contrast-Enhanced Ultrasound in the Evaluation of Abdominal Solid Organ Injuries in Pediatric Trauma Patients
Protocol Date	October 16, 2019
Protocol Version	Version 4
OBJECTIVES	

 To improve the ultrasonic visualization of abdominal solid organ injuries in children 	
METHODOLOGY	
Study Design	Prospective non-randomized cohort
Treatments	Lumason intravenous contrast
Treatment Duration	50 to 90 minutes
Study Drug and Formulation	Lumason is provided by the manufacturer (Bracco Diagnostics) in single use 5 mL vials.
Dose and Route of Administration	Dosing and Administration information can be found in section 3.4.
Concomitant and Excluded Therapy	There are no concomitant or excluded therapies.
SUBJECT POPULATION	
Number Planned	132 subjects are to complete this study: all in the treatment arm. Each patient will have at least one injured organ and their other organs will serve as controls compared to the other study subjects. Any subjects who do not complete the study will not count toward this number.
Major Inclusion Criteria	
 Age 8 to 17 years inclusive Abdominal solid organ injury visualized on computerized tomography Hemodynamically stable

October 16, 2019

Confidential

Name of Sponsor	[name], MPH
Coordinating Center	Boston Children's Hospital
Investigational Product	Lumason
ASSESSMENTS	
Efficacy	Lumason will be considered efficacious if $\geq 90\%$ of the abdominal solid organ injuries identified on computerized tomography are able to be visualized on contrast enhanced ultrasound.
Pharmacokinetics and Pharmacodynamics	No pharmacokinetics or pharmacodynamics will be performed.
Safety	Study subjects will be monitored for the development of any adverse reactions for 30 minutes following the final infusion of Lumason. No laboratory or other imaging studies are planned.
STATISTICAL METHODS AND ANALYSIS	
Efficacy	Lumason will be considered efficacious if $\geq 90\%$ of the abdominal solid organ injuries identified on computerized tomography are able to be visualized on contrast enhanced ultrasound.
Pharmacokinetics and Pharmacodynamics	No pharmacokinetics or pharmacodynamics will be performed.
Safety	Study personnel will monitor subjects for 30 minutes following the last infusion of Lumason. Patients will be maintained on a cardiopulmonary monitor through this time period. All adverse events will be graded according to the criteria specified by the Common Terminology Criteria for Adverse Events (CTCAE) Version 4.03 (NIH, June 14, 2010).

TABLE OF CONTENTS

	Page
ABBREVIATIONS AND DEFINITIONS	7
1. BACKGROUND	8
1.1 Name and Description of Investigational Product	9
1.2 Results of Nonclinical Studies	10
1.3 Results of Clinical Studies	10
2. STUDY OBJECTIVES.....	11
3. INVESTIGATIONAL PLAN.....	12
3.1 Overall Study Design and Plan	12
3.1.1 Study Endpoints	12
3.2 Discussion of Study Design, Including Choice of Control Groups	13
3.3 Selection of Study Population.....	13
3.3.1 Inclusion Criteria	14
3.3.2 Exclusion Criteria	14
3.3.3 Removal of Subjects from Therapy or Assessment.....	14
3.3.3.1 Subject Withdrawal or Early Termination	15
3.3.3.2 Planned Follow-up for Discontinued Subjects.....	15
3.4 Study drug.....	15

Injury is the most common cause of morbidity and mortality among children. Children are more susceptible to multisystem trauma than adults given their anatomic and physiologic characteristics. Computed tomography (CT) with intravenous (IV) contrast is the gold standard test for evaluating the abdomen in children with suspected injury. CT is used liberally since abdominal injuries are often suspected and difficult to rule out with history and physical examination alone. There is a 60-75% rate of normal abdominal CTs for trauma in the pediatric population reported in the literature (1). Literature suggests that children may have an increased risk of cancer related to the radiation exposure required to perform an abdominal CT. This risk may be as high as 1 in 300 in children under 5 years of age (2). In addition, there is a 1 in 200 chance of a reaction to the IV contrast agent used (3).

To date, CT is the only reliable and accurate diagnostic modality to evaluate for intra-abdominal injuries in children. Although FAST (Focused Abdominal Sonography for Trauma) exams are used frequently in adults, this test has not been demonstrated to have sufficient sensitivity to detect abdominal organ injury in the pediatric patient (4, 5). If contrast enhanced ultrasound (CEUS) improves the sensitivity and specificity of sonography in diagnosing an abdominal solid organ injury, it may become a valuable diagnostic tool, supplanting CT.

In Europe, CEUS using SonoVue, the European brand-name for Lumason, has been used clinically for more than a decade, reported mainly in adults. Valentino, et al. published results of a prospective study performed in Italy comparing the sensitivity and specificity of ultrasound and CEUS to abdominal/pelvis CT with IV contrast. A total of 27 patients were prospectively studied and they found CEUS to have a 92.9% sensitivity, 100% specificity, 100% positive predictive value (PPV) and 93.8% negative predictive value (NPV) compared to CT (6).

Valentino published a subsequent study of 133 adult trauma patients with blunt abdominal solid organ injury on CT who underwent CEUS and found 96.4% sensitivity, 98% specificity, 98.8% PPV and 94% NPV (7) compared to CT.

Clinical experience with the use of CEUS has been limited in the United States. An as yet unpublished pilot study conducted by Zalieckas et al enrolled 18 children with 21 abdominal solid organ injuries identified on CT. Children underwent greyscale and Doppler ultrasound studies, then CEUS using the contrast agent Optison. They found that greyscale/Doppler ultrasound had a 45.2% sensitivity, 96.4% specificity, a 79.2% PPV, and an 85.3% NPV compared to CT. CEUS had an 85.7% sensitivity, 98.6% specificity, 94.7% PPV and 95.8% NPV. Two of the 3 missed injuries were in one 100 kilogram pediatric patient, suggesting that further trials be limited to patients otherwise considered to be good candidates for abdominal sonography.

Optison and Lumason are both contrast agents used to perform CEUS. Lumason is now FDA-approved for use in the characterization of focal liver lesions in adult and pediatric patients. It has been studied and used in Europe, under the brand name SonoVue, to identify abdominal solid organ injuries. Because Lumason is FDA-approved for a closely related indication in a pediatric population, we have chosen to use Lumason for this study.

1.1 NAME AND DESCRIPTION OF INVESTIGATIONAL PRODUCT

Lumason (sulfur hexafluoride lipid-type A microspheres) for injectable suspension is used to prepare the ultrasound contrast agent. The single use kit contains the following three items:

- 1) one clear glass 10 mL vial containing 25 mg of lyophilized powder lipid-type A, 60.7 mg of sulfur hexafluoride gas and capped with a blue flip-cap
- 2) one prefilled syringe containing 5 mL Sodium Chloride 0.9% Injection, USP (Diluent)
- 3) one Mini-Spike

Each vial is formulated as a 25 mg sterile, pyrogen-free lyophilized powder containing 24.56 mg of polyethylene glycol 4000, 0.19 mg of distearoylphosphatidyl-choline (DSPC), 0.19 mg of dipalmitoylphosphatidylglycerol sodium (DPPG-Na) and 0.04 mg of palmitic acid. The headspace of each vial contains 6.07 mg/mL ($\pm 2\%$) sulfur hexafluoride, SF₆, or 60.7 mg per vial.

Each prefilled syringe with 5 mL of diluent 0.9% Sodium Chloride Injection is sterile, nonpyrogenic, preservative free containing 9 mg sodium chloride per mL.

Upon reconstitution with 5mL diluent, Lumason is a milky white, homogeneous suspension containing sulfur hexafluoride lipid-type A microspheres. The suspension is isotonic and has a pH of 4.5 to 7.5; it is only for intravenous administration.

The sulfur hexafluoride lipid microspheres are composed of SF₆ gas in the core surrounded by an outer shell monolayer of phospholipids consisting DSPC and DPPG-Na with palmitic acid as a stabilizer. Sulfur hexafluoride has a molecular weight of 145.9. Each milliliter of reconstituted Lumason suspension contains 1.5 to 5.6 x10⁸ microspheres, 68 mcg SF₆ (12 mcL), 0.038 mg DSPC, 0.038 mg DPPG-Na, 4.91 mg polyethylene glycol 4000 and 0.008 mg palmitic acid. The sulfur hexafluoride associated with the microspheres suspension is 45 mcg/mL. Fifteen to twenty three percent of the total lipids in the suspension are associated with the microspheres. The sulfur hexafluoride lipid microsphere characteristics are listed in the following table:

Microsphere Characteristics	
Mean diameter range	1.5 – 2.5 μm
Percent of microspheres	≤ 10 μm ≥ 99%
Upper size limit	100.0% ≤ 20 μm

1.2 RESULTS OF NONCLINICAL STUDIES

In a study reported by Tang et al using a dog model of induced liver and spleen injuries, CEUS using SonoVue showed a high level of concordance with CT (8).

1.3 RESULTS OF CLINICAL STUDIES

Preliminary Studies

Several European trials have investigated the use of CEUS to identify abdominal solid organ injuries seen on CT in children. These studies have used SonoVue, which is the European brand-name of Lumason. Sessa reported a retrospective series of 254 adults and children aged from 7

to 82 who underwent ultrasound, CEUS using SonoVue and CT to evaluate their abdomen after injury. 84 abdominal injuries were noted on CT, 50 of which were seen on ultrasound. The use of CEUS allowed the visualization of 81 of 84 injuries with no adverse events related to contrast administration (9).

Valentino et al reported a prospective study of the sensitivity and specificity of ultrasound and CEUS (CEUS) versus CT. 27 children were enrolled, with a mean age of 9 years. SonoVue was injected as a bolus followed by a normal saline bolus. 12 patients had 14 abdominal solid organ injuries seen on CT. 13 injuries were identified on CEUS (sensitivity 92.9%, specificity 100%, PPV 100%, NPV 93.8%). No adverse events were reported from contrast administration (10).

Menichini et al reported a retrospective series of 73 children who presented to a single emergency department with concern for an abdominal injury. 67 of the 73 children had an abdominal solid organ injury, only 26 of which were seen on standard ultrasound. Using CEUS with two 1.2 mL doses of SonoVue all 67 solid organ injuries seen on CT were able to be seen for a sensitivity, specificity, PPV and NPV of 100%. No adverse events were noted related to the SonoVue administration (11).

Rosado and Riccabona reviewed the off-label use of intravenous ultrasound contrast in 502 children distributed over 19 published studies (12). The most common agent used was SonoVue, in 447 children, and the second most common reason was to identify abdominal solid organ injuries. Ten patients (2%) were reported to have an adverse event, with 9 of the events being minor and transient. One patient (0.2%) suffered an anaphylactic reaction to the contrast agent and this resolved with proper treatment (12). This adverse event profile compared favorably to that seen with CT contrast (13).

2. STUDY OBJECTIVES

The primary goal of the study is to evaluate whether the use of ultrasound contrast can improve the sensitivity and specificity of ultrasound in diagnosing abdominal solid organ injuries in pediatric patients, thereby making it a valuable diagnostic tool.

Since all patients entered on the study will have CT positive results, the primary endpoint is the proportion of patients for whom all organs identified by CT with injuries are also identified by CEUS, regardless of injury grade. This will provide an estimate of the sensitivity assuming CT as the gold standard.

The secondary objectives are to determine: 1) for each organ, the proportion of patients for whom the organ is identified by CT and CEUS as injured, 2) proportion of injuries identified by CEUS which are within 1 grade of the injury identified by CT, 3) the proportion of patients where the absence or presence of peritoneal fluid identified by CT is also identified by CEUS, and 4) the comparison between ‘real-time’ and centralized interpretation of CEUS images.

3. INVESTIGATIONAL PLAN

3.1 OVERALL STUDY DESIGN AND PLAN

To address the primary objective, we propose a multi-center study with participation from 7-10 sites to enroll 132 subjects who complete the study aged 8-17 over 2-3 years. [name] is the Sponsor Investigator, with Boston Children’s Hospital acting as the coordinating center. Prior to enrollment, each subject will have already undergone an abdominal CT that identified at least one solid organ abdominal injury. As part of the study, subjects will undergo a greyscale/Doppler ultrasound and CEUS within 48 hours of injury. The study will measure the number of organ injuries identified, and the severity of organ injury. The ultrasound studies will be performed by a radiologist who is blinded to the results of the CT. The findings on greyscale/Doppler ultrasound and CEUS will be compared to the CT, using the CT findings as the standard.

3.1.1 Study Endpoints

- Primary endpoint is the proportion of patients for whom all organs identified by CT with injuries are also identified by CEUS, regardless of injury grade.
- Secondary endpoints:
 - For each organ, the proportion of patients for whom the organ is identified by CT and CEUS as injured.

- The proportion of injuries identified by CEUS which are within 1 grade of the injury identified by CT.
- The proportion of patients where the absence or presence of peritoneal fluid identified by CT is also identified by CEUS.
- The proportion of patients with agreement between ‘real-time’ and centralized interpretation of CEUS images.

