3.5.2 Assessment of Efficacy

The presence or absence of an injury as well as the grade of the injury will be determined for the liver, spleen, pancreas, and each kidney in each patient. In addition, the presence or absence of peritoneal fluid as well as a rough estimate of the amount of fluid will be determined for each patient. These data will be determined by a sonographer for each of the study subjects. Inter-rater reliability will be determined by comparing the “real-time” read to a central read. These data will then be compared to the findings on computerized tomography, using the tomography as the standard. Sensitivity and specificity of the sonograms and the CEUS to identify injuries diagnosed on computerized tomography will be determined. Lumason will be considered effective if $\geq 90\%$ of the injuries identified by CT are visualized by CEUS.

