3.8.2 Statistical Analysis Plan

We will summarize patient demographic and clinical characteristics using descriptive statistics: means, standard deviations, medians, and ranges for continuous measures; frequencies and proportions for categorical measures. For the primary objective, we will calculate the proportion and 95% confidence interval. For the secondary objectives, we will calculate the proportion and 95% confidence interval. We will also report the sensitivity and specificity of the CEUS relative to CT in identifying individual organ abnormalities in separate models and combined models. In the combined analysis, sensitivity and specificity will be estimated using random effects model or generalized estimating equations to adjust for potential correlation between organs within an individual. Statistical analysis will be performed using standardized packages (SPSS version 19.0 from SPSS Inc./IBM, Chicago, IL or SAS version 9.4 from SAS Institute Inc., Cary, NC.)

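### The peritoneal-fluid endpoint is one overall agreement figure, which depends on how common fluid is and cannot show which error CEUS makes; sensitivity and specificity for fluid should be reported separately.

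*Combined protocol and SAP*

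**What the plan says.** Section 2 gives the third secondary objective as "the proportion of patients where the absence or presence of peritoneal fluid identified by CT is also identified by CEUS", and section 3.1.1 repeats it as an endpoint: "The proportion of patients where the absence or presence of peritoneal fluid identified by CT is also identified by CEUS". A child counts as a success if CT and CEUS both show fluid or both show none, and every child is in the denominator. The reference is CT; section 3.1 describes the comparison as "using the CT findings as the standard".

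Section 3.8.2 gives the analysis: "For the secondary objectives, we will calculate the proportion and 95% confidence interval". It then adds: "We will also report the sensitivity and specificity of the CEUS relative to CT in identifying individual organ abnormalities". Section 3.5.2 has a parallel statement: "Sensitivity and specificity of the sonograms and the CEUS to identify injuries diagnosed on computerized tomography will be determined". Neither statement names fluid. No kappa, predictive value or split by CT fluid status is planned for it.

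The data for a split will exist. Section 3.5.2 says that "the presence or absence of peritoneal fluid as well as a rough estimate of the amount of fluid will be determined for each patient", and section 3.5.2.2 has the sonographer record fluid at both the greyscale/Doppler and the contrast examination.

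**The concern.** Overall agreement averages sensitivity and specificity, weighted by the share of children with and without fluid on CT. This has two consequences.

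- The same reader performance gives different headline figures in cohorts with different fluid prevalence, so the result is hard to carry to another population.
- One number cannot separate missed fluid from fluid called where CT shows none. If fluid is very common or very rare, the rarer group has little weight and poor performance in it hardly shows.

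The trial enrols only children with a solid organ injury on CT, so fluid prevalence may be far from 50%, but the documents do not give it. Fluid is not an entry criterion (section 3.3.1), so the cohort can contain both CT fluid-positive and CT fluid-negative children. For fluid, both accuracy measures can then be estimated at patient level, and pooling sets that information aside. At stake is how one secondary result can be read.

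**Working it through.** **Inputs from the documents.** N = 132 and a maximum 95% interval width of 17.6% for secondary endpoints (section 3.8.1); exact Clopper-Pearson limits, as that section uses for the primary endpoint; CT as reference (section 3.1). Fluid prevalence, and CEUS sensitivity and specificity for fluid, are not given. All values used for them below are assumptions.

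**Step 1: reproduce the plan's precision figures.** For n = 132 the widest Clopper-Pearson interval is at 66/132: 41.18% to 58.82%, width 17.64%, which matches the stated 17.6%. At 90% observed (118.8/132) the limits are 83.57% and 94.54%, which match the stated 83.6% and 94.5%. The plan's arithmetic is sound; the point concerns the endpoint definition.

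**Step 2: what the endpoint measures.** With prevalence p, sensitivity Se and specificity Sp,

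agreement = p × Se + (1 − p) × Sp.

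Its slope in p is Se − Sp, so it is free of prevalence only when Se = Sp.

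**Step 3: dependence on prevalence.**

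| Assumed Se / Sp | p = 30% | p = 50% | p = 80% | p = 90% |
|---|---|---|---|---|
| 95% / 50% | 63.5% | 72.5% | 86.0% | 90.5% |
| 98% / 20% | 43.4% | 59.0% | 82.4% | 90.2% |

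For example, 0.30 × 0.95 + 0.70 × 0.50 = 0.635, and 0.90 × 0.95 + 0.10 × 0.50 = 0.905. The first row moves by 27 points (0.60 × 0.45) with no change in reader performance.

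**Step 4: the type of error is hidden.** At p = 50%, Se 95% with Sp 30% gives 0.5 × 0.95 + 0.5 × 0.30 = 62.5%. Exchanging the two gives the same 62.5%. The two readers make opposite errors and have the same endpoint value.

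**Step 5: limiting case.** If fluid is called in every child (Se 100%, Sp 0%, kappa 0), agreement equals prevalence.

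- With 119 of 132 CT-positive, agreement is 90.2% (exact 95% CI 83.7% to 94.7%), and all 13 CT-negative children are misread.
- With 106 of 132 it is 80.3% (72.5% to 86.7%).
- With 66 of 132 it is 50%.

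**Step 6: a less extreme table at 90% prevalence.** Suppose 113 of 119 CT-positive and 4 of 13 CT-negative children are read correctly.

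- Agreement: 117/132 = 88.6% (82.0% to 93.5%)
- Sensitivity: 113/119 = 95.0% (89.3% to 98.1%)
- Specificity: 4/13 = 30.8% (9.1% to 61.4%)
- Negative predictive value: 4/(4 + 6) = 40%
- Kappa: 0.29

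**Step 7: precision after the split.** Each proportion has its own denominator. Worst-case Clopper-Pearson widths for the smaller group are:

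| Assumed prevalence | Smaller group | Worst-case width |
|---|---|---|
| 50% | 66 | 25.1% |
| 70% | 40 | 32.4% |
| 80% | 26 | 40.1% |
| 90% | 13 | 55.6% |

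**The case against.** The strongest reply is that the effect may be small. Masking needs fluid to be very common or very rare, and the documents do not say that it is either. At 50% prevalence the two accuracy pairs in the table give 72.5% and 59.0%, which nobody would take for good performance, and if sensitivity and specificity are similar the pooled figure does little harm. This stands as a limit on size. It does not change what the endpoint measures or supply the missing split.

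A second reply is that fluid status is recorded for every child, so the 2×2 table could be added at reporting. That is also true: no information is lost. But the plan does not commit to the table, and its statements on sensitivity and specificity are confined to injuries and organ abnormalities.

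A third reply is that the split is weakest where it matters most. At 80% to 90% prevalence the CT-negative group is only about 26 to 13 children and its interval is very wide. This is a real cost. The pooled interval does not show that uncertainty.

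Three stronger readings are tempting, and the documents do not support them.

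- A reader might infer that CEUS could score well here while unable to rule fluid in or out. The two accuracy pairs do not show that: the negative likelihood ratio is 0.05/0.50 = 0.10 and 0.02/0.20 = 0.10, so a negative CEUS would still cut the odds of fluid tenfold. They show poor specificity. Only the limiting case in step 5 is uninformative, and nothing suggests that it will occur.
- A reader might infer that sonographers will over-call fluid because every enrolled child is CT-positive. Sections 3.1, 3.2 and 3.5.1 blind them to the CT result, and section 3.5.1 also to the medical records. Even if they infer eligibility, it implies a solid organ injury and not fluid.
- A reader might infer that the efficacy conclusion is at risk. The 90% criterion applies to injuries and to the primary endpoint; the fluid endpoint has no success threshold.

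**Conclusion.** The point holds as a low-cost improvement to one secondary endpoint. As written, the endpoint mixes two error types in proportions set by an unstated prevalence, and no other part of the plan gives sensitivity or specificity for fluid. That follows from the definition and needs no assumption about how readers behave.

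The size is conditional. Under an assumed 95% sensitivity and 50% specificity, agreement runs from 63.5% to 90.5% as assumed prevalence runs from 30% to 90%. The effect vanishes if sensitivity equals specificity, and a high figure can conceal a poor component only when fluid is very common or very rare. The primary endpoint, the sample size of 132, the futility rule and the efficacy criterion are unaffected.

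**What to change.** In sections 3.1.1 and 3.8.2 (and the matching objective in section 2), replace the single fluid proportion by two, each with an exact 95% confidence interval:

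- CEUS fluid-positive among children with fluid on CT;
- CEUS fluid-negative among children without fluid on CT.

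Show the CT-by-CEUS 2×2 table, and keep overall agreement as a supplementary line beside the observed prevalence.

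In section 3.8.1, state that the 17.6% maximum width applies to proportions based on all 132 children and not to these two denominators, and give the worst-case widths: about 25% for 66 children, 40% for 26 and 56% for 13.

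The cost is a few sentences and one table. No new data, visits or patients are needed. The downside is that the smaller group's estimate may be very imprecise, and the report should say so.
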